[§] **End of Treatment/Withdrawal:** Visit to be performed as soon as possible but no later than 4 weeks from the last dose of investigational products and prior to initiation of any new anti-tumor therapy. Obtain assessments if not completed during the previous 4 weeks on study (or within the previous 8 weeks or 12 weeks [as applicable] for disease assessments).

[□] **Post Treatment Follow-up:** At least 28 days, and no more than 35 days after discontinuation of treatment patients will return to undergo review of concomitant medications, vital signs, ECOG, abbreviated physical exam, and assessment for resolution of any treatment related toxicity. Patients continuing to experience toxicity at this point following discontinuation of treatment will continue to be followed at least every 4 weeks until resolution or determination, in the clinical judgment of the investigator, that no further improvement is expected.

- Informed Consent:** Informed consent must be obtained prior to any protocol required assessments.
- Medical/Oncological History:** To include information on oncology disease including details of diagnosis and prior anticancer treatments (systemic treatment, prior surgery and radiotherapy, etc). When available primary diagnosis history should also include known molecular characteristics of the patient's tumor including mutations, amplifications, etc.
- Baseline Signs/Symptoms:** Baseline tumor related signs and symptoms will be recorded at the Cycle 1, Day 1 (C1D1) visit prior to initiating treatment and then reported as adverse events during the trial if they worsen in severity or increase in frequency.
- Physical Examination (PE):** A full physical examination including an examination of all major body systems and breasts, height (at screening only), weight, blood pressure and pulse rate, which may be performed by a physician, registered nurse or other qualified health care provider, as acceptable according to local regulation. Physical examinations will be carried out at Screening and the End of Treatment.
- Abbreviated PE:** A symptom directed exam and an assessment for emergent toxicities or changes from prior visits conducted by a physician, trained physician's assistant or nurse practitioner, as acceptable according to local regulation.
- Vital Signs:** blood pressure and heart rate should be recorded after approximately 5 minutes of rest.

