6.4. Patient Withdrawal

Withdrawal of consent:

Patients who request to discontinue receipt of study treatment will remain in the study and must continue to be followed for protocol specified follow-up procedures. The only exception to this is when a patient specifically withdraws consent for any further contact with him or her or persons previously authorized by the patient to provide this information. Patients should notify the investigator in writing of the decision to withdraw consent from future follow-up, whenever possible. The withdrawal of consent should be explained in detail in the medical records by the investigator, as to whether the withdrawal is only from further receipt of investigational product or also from study procedures and/or posttreatment study follow-up, and entered on the appropriate CRF page. In the event that vital status (whether the patient is alive or dead) is being measured, publicly available information should be used to determine vital status only as appropriately directed in accordance with local law.

Lost to follow-up:

All reasonable efforts must be made to locate patients to determine and report their ongoing status. This includes follow-up with persons authorized by the patient as noted above. Lost to follow-up is defined by the inability to reach the patient after a minimum of 2 documented phone calls, faxes, or e-mails as well as lack of response by the patient to 1 registered mail letter. All attempts should be documented in the patient's medical records. If it is determined that the patient has died, the site will use locally permissible methods to obtain the date and cause of death. If the investigator's use of a third-party representative to assist in the follow-up portion of the study has been included in the patient's informed consent, then the investigator may use a sponsor-retained third-party representative to assist site staff with obtaining the patient's contact information or other public vital status data necessary to complete the follow-up portion of the study. The site staff and representative will consult publicly available sources, such as public health registries and databases, in order to obtain updated contact information. If, after all attempts, the patient remains lost to follow-up, then the last-known-alive date as determined by the investigator should be reported and documented in the patient's medical records.

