- Progression Free Survival (PFS)** - is defined as the time from Cycle 1 Day 1 (CID1) to first documentation of disease progression or death due to any cause, whichever occurs first. Patients last known to be **1) alive** 2) on treatment or within the post-treatment follow-up period and 3) progression-free, are censored at the date of the last disease assessment that verified lack of disease progression. Patients who start new anti-cancer treatment prior to the end of post-treatment follow-up period and have adequate baseline and on-treatment objective disease assessments without evidence of progressive disease are censored at the date of the last objective disease assessment. Patients with inadequate baseline or no on-study disease assessments are censored at CID1 unless death occurred prior to the first planned assessment (in which case the death is an event). Patients with at least one on-study disease assessment who discontinue treatment without disease progression and without death within 28 days of discontinuation are censored at the date of the last objective disease assessment that verified lack of disease progression (if progression or death is within 28 days of discontinuation the progression or death is an event). Patients with documentation of progression or death after an unacceptably long interval (>16 weeks) since the previous disease assessment will be censored at the time of the previous assessment. If applicable, patients who are still ongoing at time of study termination by sponsor are censored at the date of study termination.

 $PFS \text{ (days)} = [\text{progression/death date} - \text{CID1} + \mathbf{1}]$.

If last adequate tumor assessment is within 6 months of CID1, any event of death or progression occurring after more than 18 weeks of last tumor assessment, then it qualifies for 2 missing and we censor at last adequate tumor assessment.

If last adequate tumor assessment is after 6 months and before 24 months of CID1, any event of death or progression occurring after more than 26 weeks of last tumor assessment, then it qualifies for 2 missing and we censor at last adequate tumor assessment.

If last adequate tumor assessment is after 24 months of CID1, any event of death or progression occurring after more than 4 months and 2 weeks of last tumor assessment, then it qualifies for 2 missing and we censor at last adequate tumor assessment.

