- **Duration of Response (DOR):** Time from the date of first documentation of CR or PR to the date of first documentation of objective progression or death due to any cause.
- **Time to Progression (TTP):** Time from randomization until disease progression.

More details of censoring are provided in [Appendix 3](#).

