- If CR determination depends on a residual lesion that decreased in size but did not disappear completely, it is recommended the residual lesion be investigated with biopsy or fine needle aspirate. If no disease is identified, objective status is CR.

- If progression determination depends on a lesion with an increase possibly due to necrosis, the lesion may be investigated with biopsy or fine needle aspirate to clarify status.

Subjective Progression

Patients requiring discontinuation of treatment without objective evidence of disease progression should not be reported as PD on tumor assessment CRFs. This should be indicated on the end of treatment CRF as off treatment due to Global Deterioration of Health Status. Every effort should be made to document objective progression even after discontinuation of treatment.

Table 4 Objective Response Status at each Evaluation

Target Lesions	Non-target Disease	New Lesions	Objective status
CR	CR	No	CR
CR	Non-CR/Non-PD	No	PR
CR	NE or Missing	No	PR
PR	Non-CR/Non-PD, NE or Missing	No	PR
SD	Non-CR/Non-PD, NE or Missing	No	Stable
NE or Missing	Non-PD	No	NE
PD	Any	Yes or No	PD
Any	PD	Yes or No	PD
Any	Any	Yes	PD

If the protocol allows enrollment of patients with only non-target disease, the following table will be used:

Table 5 Objective Response Status at each Evaluation for Patients with Non-Target Disease Only

Non-target Disease	New Lesions	Objective status
CR	No	CR
Non-CR/Non-PD	No	Non-CR/Non-PD
NE	No	NE
Unequivocal progression	Yes or No	PD
Any	Yes	PD

Best Overall Response

The best overall response (BOR) is the best response recorded from the randomization until disease progression or death due to any cause. This is derived from the sequence of objective

statuses. Objective statuses are not considered after objective progression is documented or after start of the first anticancer treatment post discontinuation of protocol treatment. BOR for each patient will be derived as one of the following categories.

- **Complete response (CR):** At least one objective status of CR documented before progression.
- **Partial response (PR):** At least one objective status of PR documented before progression.
- **Stable disease (SD):** At least one objective status of stable documented at least 8 weeks after randomization date and before progression but not qualifying as CR, PR.
- **Progressive Disease (PD):** Objective status of progression within 16 weeks of randomization, not qualifying as CR, PR or SD.

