11.3. APPENDIX 3: CENSORING DETAILS**Table 6** Progression Free Survival and Duration of Response

Situation	Date of Progression/Censoring ¹	Outcome
Inadequate baseline assessment	Start date (CIDI)	Censored
No on-study assessments	Start date (CIDI)	Censored
Alive, on treatment ² and no Progression	Date of last objective tumor assessment	Censored
Progression Documented on or between scheduled tumor assessments prior to treatment discontinuation ²	Date of first objective tumor assessment showing objective progression	Progressed (Event)
Treatment discontinuation for undocumented progression	Date of last objective tumor assessment prior to discontinuation ²	Censored
Treatment discontinuation due to toxicity or other reason	Date of last objective tumor assessment prior to discontinuation ²	Censored
Death prior to first planned tumor assessment	Date of death	Death (Event)
Death without objective progression prior to treatment discontinuation ²	Date of death	Death (Event)
Death or progression after 2 or more missed tumor assessments	Date of last objective tumor assessment prior to the event	Censored
Ongoing at time of study termination by sponsor	Date of study termination	Censored

1: For date of censorship, if a tumor assessment takes place over a number of days (eg, superficial lesions one day, scans another), the last date is used as the assessment date.

2: or within 28 days of discontinuation of treatment.

Table 7 Time to Progression

Situation	Date of Progression/Censoring ¹	Outcome
Inadequate baseline assessment	Start date (CIDI)	Censored
No on-study assessments	Start date (CIDI)	Censored
Alive, on treatment ² and no Progression	Date of last objective tumor assessment	Censored
Progression Documented on or between scheduled tumor assessments prior to treatment discontinuation ²	Date of first objective tumor assessment showing objective progression	Progressed (Event)
Treatment discontinuation for undocumented progression	Date of last objective tumor assessment prior to discontinuation ²	Censored
Treatment discontinuation due to toxicity or other reason	Date of last objective tumor assessment prior to discontinuation ²	Censored
New anticancer treatment <28 days after discontinuation of treatment without progression	Date of last objective tumor assessment prior to new anticancer treatment	Censored
Death prior to first planned tumor assessment	Start date (CIDI)	Censored

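### PFS, DOR and TTP count post-treatment events only within 28 days of stopping; for patients who stop for clinical deterioration this censoring is informative and pushes the curves upward

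*SAP*

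**What the plan says.** SAP 7.1 defines PFS as time from Cycle 1 Day 1 to documented progression or death from any cause. It ends DOR at "first documentation of objective progression or death due to any cause". It defines TTP to progression only.

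For patients who stop treatment, 7.1 states: "Patients with at least one on-study disease assessment who discontinue treatment without disease progression and without death within 28 days of discontinuation are censored" as of the last objective assessment that showed no progression. A parenthesis adds the window: "if progression or death is within 28 days of discontinuation the progression or death is an event".

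SAP Appendix 3 repeats this in Table 6 (PFS and DOR) and Table 7 (TTP). The event rows for progression, and in Table 6 for death, refer to the time before treatment discontinuation, extended by footnote 2: "or within 28 days of discontinuation of treatment". The row "Treatment discontinuation for undocumented progression" and the row for toxicity or other reasons are both censored at the last objective scan. In Table 6 a death before the first planned assessment is an event; in Table 7 no death is.

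Both RECIST appendices (Protocol Appendix 4, SAP Appendix 2) say that stopping without objective evidence is not progression and is recorded as Global Deterioration of Health Status. They then add: "Every effort should be made to document objective progression even after discontinuation of treatment".

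SAP 9.2.2.1 and Table 3 plan Kaplan-Meier summaries under these rules, with no sensitivity analysis.

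**The concern.** The endpoint definitions take no account of treatment status, but the censoring rule does. A progression found on day 29 after stopping meets the definition of a PFS event and is still discarded, with the patient censored back at the last clean scan.

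Kaplan-Meier treats censored patients as having the same future risk as those still followed. That is hard to defend for someone taken off treatment because they were visibly worsening. Such patients leave the risk set as progression-free, and the curve for those who remain looks better than the arm really did. Part 2 is non-randomised, so no control arm is subject to the same rule. Part 2 is also where the efficacy summaries are produced; Part 1 efficacy is only listed.

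**Working it through.** The documents state no PFS, DOR or TTP target, event count or discontinuation rate, so there is no plan figure to reproduce. The check has three parts.

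**1. Definition against counting rule**

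| Endpoint | Defined to | Counted after stopping |
|---|---|---|
| PFS | progression or any death | within 28 days, plus death before the first planned assessment |
| DOR | progression or any death | within 28 days |
| TTP | progression | progression within 28 days |

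A stop for Global Deterioration of Health Status is by rule not objective progression, so it falls in a censored row unless progression or death is recorded inside the window.

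**2. Direction**

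Inputs from the Protocol Schedule of Activities: scans every 8 weeks for 6 months, then every 12 weeks. Assumed: median 4 to 9 months on treatment, 10-30% of patients stopping without objective progression, 15% of events being deaths, and a hazard after stopping equal to k times the on-treatment hazard. The comparator counts all events, with scheduled scans continuing after stopping. Simulated with 200,000 patients per scenario, the SAP rule minus the comparator at 6 months is:

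| k | Difference in 6-month PFS, points |
|---|---|
| 0.5 | -0.6 to -6.6 |
| 1 | about -0.3 to -3.1 |
| 1.5 | about 0 |
| 2 | +0.2 to +1.3 |
| 4 | +0.8 to +4.5 |
| 8 | +1.4 to +5.8 |
| 15 | +1.7 to +5.9 |

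The bias is upward only when stoppers are at clearly higher risk, at roughly twice the hazard or more. That fits deterioration. It is not established for toxicity stops, where the bias may be nil or reversed.

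**3. Size for deterioration stops**

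If a patient stops at a random point between scans L weeks apart, the chance that the next scheduled date is more than 4 weeks away is (L - 4)/L:
- 8 weeks: 4/8 = 50%
- 12 weeks: 8/12 = 67%
- 4 months (17.4 weeks): 13.4/17.4 = 77%

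Assume 20% of patients stop for deterioration at the time of true progression, none is scanned before the next scheduled date, and every later scan is obtained. About 61-66% of these patients' progressions then fall outside the window. 12-month PFS becomes:

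| True median | SAP rule | Later scan counted | Gap, points |
|---|---|---|---|
| 5 months | 25.3% | 21.4% | 3.9 |
| 8 months | 42.5% | 38.3% | 4.2 |
| 12 months | 57.4% | 53.3% | 4.1 |

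These runs used 20,000 patients each; repeats with 200,000 give the same gaps to within 0.1 point. At 10% stopping the gaps are 1.7 to 2.2 points, and at 30% they are 5.8 to 6.6.

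Now let a share of these patients be scanned about 2 weeks after stopping, still at 20% stopping:
- 50% scanned: gap about 2 points
- 80% scanned: about 0.8
- 100% scanned: 0

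For scale, the binomial standard error at 50% PFS is sqrt(0.25/40) = 7.9 points in Arm A and sqrt(0.25/30) = 9.1 points in Arms B and C.

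**The case against.** The strongest reply is Protocol 7.4. It asks for a tumour assessment whenever progression is suspected, naming symptomatic deterioration, and at withdrawal if there was none in the previous 8 weeks. A patient who stops for deterioration should therefore be scanned near that date, and progression seen within 28 days counts. This stands, and it makes the 4-point gap and the 61-66% upper-end figures. It does not remove the defect. Scans are not always done promptly, progression may not be measurable at the first one, and the plan has no analysis that would show the difference.

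Several stronger readings are tempting but not supported:

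- A reader might infer that every post-treatment event beyond 28 days is lost. Deaths before the first planned assessment are PFS events, and deaths never count in TTP.
- A reader might infer that the visit 28 to 35 days after stopping yields progression data that are then discarded. No scan is scheduled at that visit.
- Protocol 6.4 says "Patients who request to discontinue receipt of study treatment will remain in the study and must continue to be followed", which might suggest continued imaging. The sentence goes on to limit this to the follow-up procedures the protocol specifies, and no scan is scheduled after end of treatment.
- A reader might contrast the rule with a progression found 17 weeks after the last scan on treatment, as if that clearly counted. SAP 7.1 also censors events after a gap of more than 16 weeks, so its own limits conflict.
- A reader might infer that PFS is judged against a historical benchmark. The readable text uses historical data only for sample size.

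It is also fair that progression, death and last-assessment dates are listed, discontinuation reasons are tabulated, and DOR events and censorings are counted.

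**Conclusion.** The point holds in limited form. The 28-day rule departs from the stated PFS and DOR definitions and from the effort both RECIST appendices ask for; TTP carries the same limit for progression. For deterioration stops the censoring is informative and upward. For other stops the direction is unknown, so a general claim that all three curves read too high is not supported.

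The size cannot be fixed from the documents. At an assumed 20% of deterioration stops, 12-month PFS is overstated by 0 to about 4 points, depending on how many patients are scanned promptly. That is below one standard error per arm, but it is systematic and does not shrink with more patients. PFS, DOR and TTP are secondary in Part 2 and no hypothesis is tested. ORR, the Part 2 primary activity measure, does not depend on this rule. It is worth correcting because the correction is cheap.

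**What to change.** 1. In SAP 7.1, reconcile the sentence that censors after more than 16 weeks with the limits of 18 weeks, 26 weeks, and 4 months plus 2 weeks. The first two of these equal two scan intervals plus 2 weeks (2 x 8 + 2 = 18; 2 x 12 + 2 = 26), whereas the third allows only one 4-month interval plus 2 weeks. Step 2 cannot be programmed until this is settled.
2. Add a PFS, DOR and TTP analysis that counts every recorded objective progression (and death, for PFS and DOR) on its own date regardless of discontinuation, provided it precedes new anticancer therapy and lies within the reconciled missed-scan limit.
3. Add a supplementary PFS and DOR analysis that counts discontinuation for Global Deterioration of Health Status as an event on the discontinuation date. The end-of-treatment CRF already carries this reason.
4. Report, per arm, the number censored by discontinuation reason.

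The cost is SAP wording and a little extra programming, with no new visits or patients. Estimates may come out slightly shorter. Late events can be counted only where scans were obtained: if half or a quarter of the later scans exist, the recoverable part of the 4-point gap is about 2 or 1 points. Step 3 does not depend on later scans, which is the reason to run both.

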Appendix 8. Study Procedures After Primary Completion Date (PCD) Until End of
Trial..... 182

SCHEDULE OF ACTIVITIES (PART 1, PART 2 AND J-LIC)

The schedule of activities table provides an overview of the protocol visits and procedures. Refer to the [ASSESSMENTS](#) section of the protocol for detailed information on each assessment required for compliance with the protocol.

The investigator may schedule visits (unplanned visits) in addition to those listed in the schedule of activities in order to conduct evaluations or assessments required to protect the well-being of the patient.

See [Appendix 6](#) for alternative measures during public emergencies including the COVID-19 pandemic.

Protocol Activity	Screening	Active Treatment Phase [†] - One Cycle = 28 days					End of Treatment/ Withdrawal [§]	Post-Treatment Follow-Up [*]
		Cycles 1 and 2			Cycles ≥3			
Study Day	Within 28 days prior to registration unless specified otherwise	Day 1 [‡]	Day 8	Day 15	Day 21	Day 1		
Visit Window				±3 days	±3 days	±3 days	±5 days	
Informed Consent ¹	X							
Medical/Oncological History ²	X							
Baseline Signs/Symptoms ³		X						
Physical Examination ⁴	X						X	
Abbreviated Physical Examination ⁵		X	X	X	X	X		X
Vital Signs ⁶	X	X	X	X	X	X	X	X
Contraception Check ⁷	X	X				X	X	
ECOG Performance Status ⁸	X	X				X	X	X
12-Lead ECG ⁹	X	X	X C1 ⁹ and C2 ⁹	X C1 only		X	X	
Laboratory Studies¹⁰								
Hematology	X	X	X	X	X	X	X	(X)
Blood Chemistry	X	X	X ¹¹	X ¹¹	X ¹¹	X	X	(X)
Coagulation	X	X						(X)
Urinalysis	X						X	(X)
Pregnancy test	X	X				X	X	
Viral disease screening ¹²	X							
Disease Assessment								
Tumor markers (for breast cancer: CA 15-3 and CEA; Part 1 only for ovarian cancer: CA 125)	X	X				X	X	
CT/MRI Scans of Chest, Abdomen, Pelvis, any clinically indicated sites of	X	Performed every 8 weeks from C1D1 (±7 days) for the first 6 months, and then every 12 weeks (±7 days)					X ¹³	

Protocol Activity	Screening	Active Treatment Phase [†] - One Cycle = 28 days					End of Treatment/ Withdrawal [§]	Post-Treatment Follow-Up [*]
		Cycles 1 and 2				Cycles ≥3		
Study Day	Within 28 days prior to registration unless specified otherwise	Day 1 [‡]	Day 8	Day 15	Day 21	Day 1		
Visit Window			±3 days	±3 days	±3 days	±5 days		±7 days
disease, and of bone lesions; Clinical evaluation of superficial disease ¹³ Follow up for Overall Survival (OS)		thereafter for up to 2 years. After 2 years, performed every 4 months thereafter.						
Study Treatment								

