Death without objective progression prior to treatment discontinuation ²	Date of last objective tumor assessment prior to death	Censored
Progression after 2 or more missed	Date of last objective tumor assessment	Censored

tumor assessments	orior to the event	
Ongoing at time of study termination by sponsor	Date of study tennination	Censored

1: For censoring date, if a tumor assessment takes place over a number of days (eg, superficial lesions one day, scans another), the last date is used as the assessment date.
 2: or within 28 days of discontinuation of treatment.

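### SAP 7.1 gives two conflicting gap rules for censoring PFS, and both censor some events after a single missed scan although Appendix 3 requires two

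*SAP*

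**What the plan says.** The PFS definition in SAP 7.1 states that progression or death "after an unacceptably long interval (>16 weeks) since the previous disease assessment will be censored at the time of the previous assessment". This sentence is not restricted to any scan phase.

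The same definition then gives three limits, chosen by the time of the last adequate assessment:

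- Last assessment within 6 months of C1D1: an event "occurring after more than 18 weeks of last tumor assessment, then it qualifies for 2 missing".
- Last assessment between 6 and 24 months: an event "occurring after more than 26 weeks of last tumor assessment, then it qualifies for 2 missing".
- Last assessment after 24 months: an event "occurring after more than 4 months and 2 weeks of last tumor assessment, then it qualifies for 2 missing".

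In each case the patient is censored at the last adequate assessment. No sentence ranks the 16-week rule against these limits. Section 7.1 closes by pointing to Appendix 3 for further detail.

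Appendix 3 gives no number of weeks. Table 6 (PFS and DOR) censors "Death or progression after 2 or more missed tumor assessments". Table 7 (TTP) has the matching row, beginning "Progression after 2 or more missed".

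The CT/MRI row of the Protocol Schedule of Activities reads "Performed every 8 weeks from C1D1 (±7 days) for the first 6 months, and then every 12 weeks (±7 days", with the 12-week interval running to two years, and then "After 2 years, performed every 4 months thereafter". Protocol 5.4.3.3 keeps the scan calendar tied to C1D1 despite dose delays.

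**The concern.** There are two separate problems.

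(a) The 16-week sentence and the three limits give different answers for the same patient. The three limits cover different periods and do not conflict with one another. The conflict is between them and the 16-week sentence. Two programmers working from 7.1 could produce different PFS tables, and the choice might be made after the data are seen.

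(b) Each rule also censors some events after only one missed scan, where Appendix 3 asks for two or more.

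An event wrongly censored is an observed progression or death turned into a censored time at the previous scan, which lifts the PFS curve. The outputs affected are event counts, medians and Kaplan-Meier curves (SAP 9.1 and Table 3). DOR and TTP are affected only if the same week limits are applied to them. SAP version 4.0 records censoring changes in both Section 7.1 and Appendix 3, so both texts are current.

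**Working it through.** **Inputs.** Scan interval 8 weeks to month 6, 12 weeks to month 24, then 4 months (Schedule of Activities). Window ±1 week on the 8- and 12-weekly scans. Conversion assumed: 1 month = 30.44/7 = 4.348 weeks, so 6 months = 26.1 weeks, 24 months = 104.4 weeks and 4 months = 17.4 weeks.

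**1. Reproduce the plan's limits.** Two missed scans should correspond to two intervals plus one week of window at each end.

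- 8-week phase: 2 × 8 + 2 = 18. Matches.
- 12-week phase: 2 × 12 + 2 = 26. Matches.
- 4-month phase: 2 × 17.4 + 2 = 36.8 weeks. The SAP has 17.4 + 2 = 19.4 weeks, which is one interval plus 2 weeks. Does not match.
- The blanket 16 weeks is 2 × 8 with no window and fits no other phase.

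**2. Apply both rules to the calendar.** Scheduled weeks are 8, 16, 24, 36, 48, 60, 72, 84, 96. The protocol does not date the first 4-monthly scan; it is taken here as 4 months after week 96, giving weeks 113.4, 130.8 and 148.2. Each row below has exactly one missed scan and progression at the next scheduled scan, so Appendix 3 counts every one as an event.

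| Last scan (wk) | Progression (wk) | Gap (wk) | 16-week sentence | Limit in 7.1 |
|---|---|---|---|---|
| 8 | 24 | 16 | event | 18: event |
| 16 | 36 | 20 | censored | 18: censored |
| 24 | 48 | 24 | censored | 18: censored |
| 36, 48, 60 or 72 | 60, 72, 84 or 96 | 24 | censored | 26: event |
| 84 | 113.4 | 29.4 | censored | 26: censored |
| 96 | 130.8 | 34.8 | censored | 26: censored |
| 113.4 | 148.2 | 34.8 | censored | 19.4: censored |

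The fourth row is problem (a). With windows the 24-week gap spans 22 to 26 weeks, so the two rules disagree throughout. They also disagree in the 8-week phase for gaps above 16 and up to 18 weeks. After month 24, an on-schedule 4-monthly progression (17.4 weeks, no scan missed) is censored by the 16-week sentence and kept by the 19.4-week limit.

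The rows where the limit censors are problem (b). They arise where the interval changes and in the 4-month tier. If 6 months is read as six 28-day cycles (24 weeks), a week-24 scan done late in its window falls under the 26-week limit and the event is kept.

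**3. Illustrative size.** The documents give no rate of missed scans, so every input here is an assumption: exponential PFS with median 6 to 12 months, 5 to 10% of scans missed independently, 0 to 30% of progressions found at unscheduled scans, 0 to 10% of events being deaths, and nobody followed past month 22. Results are scaled to 40 patients (Arm A), from 200,000 simulated patients per setting.

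- Follow-up uniform over 6 to 22 months (about 20 to 30 events): the two rules disagree on 0.4 to 1.0 events, or 0.5 to 1.6 if baseline counts as a previous assessment.
- Full 22-month follow-up (about 27 to 36 events): 0.8 to 1.9, or 0.9 to 2.5 counting baseline.
- Events censored after at most one missed scan (6 to 22 months of follow-up): 0.7 to 2.9 under the 16-week sentence, 0.4 to 1.3 under the limits.
- 12-month PFS is 0.9 to 3.1 points higher under the 16-week sentence, and 0.8 to 2.5 points higher under the limits, than when missed scans are counted.
- At 18 months the two rules differ by 0.5 to 2.7 points. With median 12 months, 10% missed and no unscheduled scans, 18-month PFS is 37.4% (16-week sentence), 34.7% (limits) and 33.0% (counting missed scans).

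**The case against.** The disagreement in the 12-week phase cannot be read away. The other points on the plan's side are these.

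- **The month-24 cases are nearly out of reach.** From 15 December 2020 (the amendment naming the present Arm A) to the planned completion date of 5 April 2023 is 841 days, or 27.6 months (120.1 weeks). From 7 June 2021 (Arm C added) it is 667 days, or 21.9 months. Weeks 130.8 and 148.2 lie beyond both. Part 1 efficacy is only listed (SAP 9.2.2.1), although Protocol 9.2.2 allows Part 1B to be pooled with Part 2. The expected 6 to 8 cycles on treatment is 5.5 to 7.4 months. This stands: these cases add little.
- **The month-24 weeks rest on an assumed calendar.** Also true. If 4 months means four 28-day cycles, an on-time gap is 16 weeks and is not censored. The third limit is still one interval plus 2 weeks (18 weeks against 2 × 16 = 32), so that flaw does not depend on the convention.
- **Section 7.1 may be defining what Appendix 3 means by missed.** Away from interval changes the 18- and 26-week limits do equal two missed scans. At the month-6 switch they label one missed scan as two, and that switch falls within the expected time on treatment.
- **The effect is small.** The simulation omits discontinuation without progression; adding an assumed 20 to 40% by 12 months lowers the disagreement to about 0.2 to 0.8 events. The 18-month example sits at the high end, landmark estimates are optional, and a 95% interval at n = 40 has half-width about 1.96 × √(0.35 × 0.65/40) = 14.8 points. This stands as a limit on importance and leaves the contradiction in place.

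**Conclusion.** The plan is wrong as written and should be corrected. Problem (a) follows directly from the text and the scan schedule: an ordinary single missed scan in the 12-week phase is censored by one sentence of 7.1 and counted by another. Problem (b) is firm at the month-6 switch (20 and 24 weeks against 18, taking 6 months as 26.1 weeks) and in the 4-month tier. The exact weeks at the month-24 switch depend on where the first 4-monthly scan is placed.

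The likely size is around one event per 40 patients, on assumed inputs only, and always toward longer PFS. With no concurrent control in these expansion arms, that shift goes straight into the reported estimate. It bears on secondary, descriptive endpoints; no hypothesis is tested and ORR does not change.

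**What to change.** Delete the 16-week sentence and replace the three fixed limits with one rule that matches Appendix 3: censor at the last adequate assessment when two or more consecutive scheduled assessments, each with its window, were missed before the event, counted on the C1D1 calendar. State in 7.1 that this rule serves PFS, DOR and TTP, so that the Appendix 3 rows and the text agree.

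The rule needs two conventions the CT/MRI row leaves open: when the first 4-monthly scan is due, and what window the 4-monthly scans carry.

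Other fixed week limits per phase should not be substituted. A flat 26 weeks for the 12-week phase, for example, still misclassifies last scans at weeks 84 and 96 under the calendar used above.

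The cost is SAP wording and one derivation program. No new data are needed.
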